5 STUDY DESIGN

5.1 Overall Design

[figure not shown]
This is a Phase 2, randomized, open-label, 2-arm study of BMS-986213 or nivolumab in combination with investigator's choice chemotherapy as L1 treatment in participants with untreated, unresectable, and either locally advanced or metastatic GC or GEJ adenocarcinoma. Approximately 250 participants will be randomized in 2 treatment arms in this global clinical study. Nivolumab monotherapy will be administered IV as either 360 mg every 3 weeks (Q3W) or 480 mg every 4 weeks (Q4W), depending on the assigned chemotherapy regimen. Relatlimab and nivolumab combination, as an FDC, will be administered as 120-mg relatlimab/360-mg nivolumab Q3W or 160-mg relatlimab/480-mg nivolumab Q4W, depending on the assigned chemotherapy regimen.

After signing the informed consent form, participants will enter the Screening Phase. A pre-treatment tumor sample is required to be submitted from all participants. Although this study will enroll participants regardless of their LAG-3 expression status ($\geq 1\%$ or $< 1\%$; no indeterminate allowed), participants must have their LAG-3 status determined prior to completion of the remaining Screening procedures. **Patients with an indeterminate LAG-3 expression status cannot be enrolled in the study.** As deemed appropriate by the Investigator, participants may complete the remaining Screening procedures in parallel to the determination of the LAG-3 status in order to minimize the duration of the Screening Phase.

The study design schematic is presented in [Figure 5.1-1](#).

Figure 5.1-1: Study Design Schematic

^a Fixed dose combination of relatlimab [anti-LAG-3] plus nivolumab

^bInvestigator Choice Chemo:

1. **XELOX:** oxaliplatin 130 mg/m² administered IV on Day 1 of each treatment cycle and capecitabine 1000 mg/m² administered orally twice daily on Days 1 to 14 of each treatment cycle, every 3 weeks
2. **FOLFOX:** oxaliplatin 85 mg/m², leucovorin 400 mg/m² and fluorouracil 400 mg/m² administered IV on Day 1 of each treatment cycle, and fluorouracil 1200 mg/m² IV continuous infusion over 24 hours daily or per local standard on Days 1 and 2 of each treatment cycle, every 2 weeks.
3. **SOX:** oxaliplatin 130 mg/m² administered IV on Day 1 of each treatment cycle and oral S-1 twice daily on Day 1 to 14 of each treatment cycle, every 3 weeks. S-1 dose was calculated according to body surface area (BSA, mg/m²/dose): BSA <1.25 m², 40 mg/dose; ≥1.25 m² and <1.5 m², 50 mg/dose; ≥1.5 m², 60mg/dose.

Abbreviations: ECOG = Eastern Cooperative Oncology Group; F/U = follow-up; GC = gastric cancer; GEJ = gastroesophageal junction; IC = informed consent; J = Japan; LAG-3 = lymphocyte activation gene 3; PD-L1 = programmed death-ligand 1; PS = performance status; Q2W = every 2 weeks; Q3W = every 3 weeks; Q4W = every 4 weeks; T = Taiwan; ROW = Rest of World

5.1.1 Screening Phase

- The Screening Phase begins by establishing the participant's initial eligibility and signing of the informed consent form within 28 days of randomization.
- Participants are enrolled using the Interactive Response Technology (IRT) system.
- A pre-treatment tumor sample is required to be submitted from all participants. The participant's tumor-associated immune cells must have an evaluable LAG-3 status (≥ 1% or < 1%; no indeterminate allowed) and must have a PD-L1 status (combined positive score [CPS] < 1 or indeterminate, CPS ≥ 1 to < 5, CPS ≥ 5). LAG-3 expression status (LAG-3 [+] or LAG-3 [-]) and PD-L1 expression status must be determined by the central lab **prior to completion of the remaining screening procedures**. As deemed appropriate by the investigator, participants may complete the remaining screening procedures in parallel to the determination of the LAG-3 and PD-L1 expression in order to minimize the duration of the Screening Phase.
- Sufficient tumor tissue (either a formalin-fixed, paraffin-embedded [FFPE] tissue block or minimum 20 positively charged slides [if 20 are not obtainable, discuss with Sponsor]) must be submitted for biomarker evaluation prior to randomization. If available, the pathology report should be submitted with the FFPE tissue block or unstained tumor tissue slides. The tumor tissue sample may be fresh or archival if obtained within 3 months prior to randomization, and

there cannot have been any systemic therapy given after the sample was obtained. Tissue must be a core needle biopsy, excisional or incisional biopsy. Fine needle biopsies are not considered adequate for biomarker review and randomization. Biopsies of bone lesions that do not have a soft tissue component or decalcified bone tumor samples are also not acceptable. If insufficient tumor tissue is provided for analysis, acquisition of additional tumor tissue (block and/or slides) for the biomarker analysis is required.

- Participant is assessed for study eligibility according to the inclusion (Section 6.1) and exclusion (Section 6.2) criteria. The detailed procedures are described in Table 2-1.

5.1.2 Treatment Phase

- The Treatment Phase begins after contacting the IRT system for randomization. The choice of chemotherapy regimen (XELOX, SOX, or FOLFOX) must be decided before contacting the IRT system for randomization.
- Participants will be randomized to either the BMS-986213 or nivolumab arm. Each arm will be given in combination with investigator's choice chemotherapy (XELOX, FOLFOX, or SOX).
- The treatment will be given until disease progression (PD) (see Section 7.3.8), unacceptable toxicity, or participant withdrawal of consent, whichever comes first.
- Stratification factors for this study are as follows:
 - LAG-3 expression ($\geq 1\%$ or $< 1\%$; no indeterminate allowed)
 - Region (Japan/Taiwan [J/T] vs rest of world [ROW])
 - PD-L1 expression status (CPS < 1 or indeterminate, CPS ≥ 1 to < 5 , CPS ≥ 5).
- Administration of study treatment is to begin within 3 calendar days of randomization.
- Each cycle will be 6 weeks in duration.
- On the day of infusion, BMS-986213 or nivolumab is to be administered first, followed by chemotherapy. The administration procedures of chemotherapy will follow local standards. **BMS-986213 or nivolumab and chemotherapy should be administered on the same day, with the following exceptions:**
 - BMS-986213 or nivolumab is allowed to be administered alone in cases where the chemotherapy has been delayed or discontinued due to toxicity.
 - Chemotherapy alone is allowed to be administered in cases where BMS-986213 or nivolumab has been delayed or discontinued due to toxicity.
 - Participants assigned to FOLFOX will have only FOLFOX administered on Day 15 of the odd-numbered cycles (ie, Cycles 1, 3, 5, etc) and Day 1 and 29 of the even-numbered cycles (ie, Cycles 2, 4, 6, etc).
- No cross-over is allowed between XELOX, SOX, and FOLFOX regimens.
- The Treatment Phase ends when the participant is discontinued from study therapy (ie, PD, unacceptable toxicity, or participant withdrawal of consent).

Study assessment data are to be collected as outlined in Table 2-2 and Table 2-3.

5.1.3 Follow-up Phase

- The Follow-up Phase begins when the decision is made to discontinue a participant from study therapy.
- Follow-up Visit 1 will be performed 30 days from the last dose (± 7 days) or coincide with the date of discontinuation (± 7 days) if date of discontinuation is greater than 42 days after last dose. Follow-up Visit 2 will be performed 100 days (± 7 days) from last dose of study treatment. Participants must be followed for at least 100 days after last dose of study treatment. Both follow-up visits should be conducted in person.
- Survival visits - The first survival follow-up visit will be performed 3 months (± 14 days) after follow-up Visit 2. Subsequent survival follow-up visits will occur every 3 months (± 14 days) thereafter. Survival follow-up visits may be conducted in clinic or by phone.

Study follow-up assessment data are to be collected as outlined in [Table 2-4](#).

5.1.4 Blinded Independent Central Review

A Blinded Independent Central Review (BICR) will be utilized in this study for determination of BICR-assessed endpoints. The BICR will review all available tumor assessment scans for all treated participants. All investigator determinations of PD will be reviewed by the BICR (see [Section 9.1.4](#)). Details of BICR responsibilities and procedures will be specified in the BICR charter.

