10.2 Populations for Analyses

For purposes of analysis, the following populations are defined below:

Population	Description
Enrolled	All participants who sign an informed consent form. This is the dataset for disposition (and select safety)
Randomized participants	All participants who are randomized to any treatment. This is the dataset for baseline demographics and select efficacy analyses.
LAG-3 positive participants	All randomized participants in the LAG-3 positive group. This is the dataset for baseline demographics and primary efficacy analyses.
Response evaluable participants	All randomized participants who had measurable lesions at baseline

Population	Description
Treated participants	All randomized participants who take at least 1 dose of study treatment. This is the dataset for safety analyses.

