10.3.2 Efficacy Analyses

Primary Endpoint	Statistical Analysis Methods

 Objective response rate (ORR) as assessed by BICR in participants who are LAG-3 positive is defined as the number of participants with a best overall response (BOR) of CR or PR divided by the number of randomized participants who are LAG-3 positive in each arm. BOR is defined as the best response designation based on the BICR, recorded between the date of randomization and the date of objectively documented progression (per RECIST 1.1 as determined by the investigator) or death, or the date of subsequent anti-cancer therapy, whichever occurs first. 	
 ORR as assessed by BICR in participants who are LAG-3 positive will be compared between the BMS-986213 in combination with chemotherapy and nivolumab in combination with chemotherapy using a two-sided Cochran-Mantel-Haenszel test stratified by region (J/T or ROW) and PD-L1 status (CPS < 1 or indeterminate, CPS ≥ 1 to <5, CPS ≥ 5) as recorded in the IRT. Associated 70% CIs for ORR difference will be calculated. Additionally, ORR along with the exact 95% CI for each arm will be calculated using the Clopper-Pearson method.⁵²
Secondary	

 Objective Response Rate (ORR) as assessed by investigator in participants who are LAG-3 positive is defined as the number of participants with a best overall response (BOR) of CR or PR divided by the number of randomized participants who are LAG-3 positive in each arm. BOR is defined as the best response designation based on the investigator, recorded between the date of randomization and the date of objectively documented progression (per RECIST 1.1) or the date of subsequent anti-cancer therapy, whichever occurs first. 	
 ORR based on investigator in LAG-3 positive population will be compared between the BMS-986213 in combination with chemotherapy vs Nivolumab in combination with chemotherapy using a two-sided Cochran-Mantel-Haenszel test stratified by region (J/T ROW) and PD-L1 status as recorded in the IRT. Additionally, ORR along with the exact 95% CI for each arm will be calculated using the Clopper-Pearson method.⁵²

Primary Endpoint	Statistical Analysis Methods

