4.1.1 Objective Response Rate

Objective Response Rate (ORR) is defined as the number of randomized subjects who achieve a best response of confirmed complete response (CR) or confirmed partial response (PR) based on BICR assessments (using RECIST v1.1 criteria) divided by the number of all randomized subjects. If the objective is for a particular population (LAG3 positive, LAG3 negative), only that population is selected. Best Overall Response (BOR) is defined as the best response, as determined by the BICR, recorded between the date of randomization and the date of objectively documented progression per RECIST v1.1 criteria or the date of subsequent therapy (including tumor-directed radiotherapy and tumor-directed surgery), whichever occurs first. For subjects without documented progression or subsequent therapy, all available response designations will contribute to the BOR determination. Confirmation of response is required at least 4 weeks after the initial response.

When the objective is specific to the investigator assessment, the above definition is altered to exchange BICR for investigator assessment in the derivation of the endpoint.

Time to Response

Time to Response (TTR) is defined as the time from randomization to the date of the first confirmed documented response (CR or PR), as assessed by the BICR. TTR will be evaluated for responders (confirmed CR or PR) only.

When the objective is specific to the investigator assessment, the above definition is altered to exchange BICR for investigator assessment in the derivation of the endpoint.

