4.1.3.1 Primary Definition of Progression-Free Survival (Accounting for Subsequent Therapy)

The primary definition of PFS (PFS truncated at subsequent therapy) is defined as the time between the date of randomization and the date of first documented tumor progression, based on BICR assessments (per RECIST v1.1 criteria), or death due to any cause, whichever occurs first.

Subjects who die without a reported progression will be considered to have progressed on the date of their death. The following censoring rules will be applied for the primary definition of PFS:

- Subjects who did not progress or die will be censored on the date of their last evaluable tumor assessment.
- Subjects who did not have any on study tumor assessments and did not die will be censored on their date of randomization.
- Subjects who receive subsequent anti-cancer therapy prior to documented progression will be censored at the date of the last evaluable tumor assessment conducted on or prior to the date of initiation of the subsequent anti-cancer therapy.

- Subjects who did not have a documented progression and received subsequent anti-cancer therapy will be censored at the date of the last evaluable tumor assessment conducted on or prior to the initiation of the subsequent anti-cancer therapy.

Censoring rules for the primary definition of PFS (PFS truncated at subsequent therapy) are presented as follows and in Table 4.1.3.1-1.

Figure 4.1.3.1-1: PFS Primary Definition

[figure not shown]

Table 4.1.3.1-1: Censoring Scheme used in Primary Definition of PFS

Situation	Date of Progression or Censoring	Outcome
No baseline tumor assessments*	Date of randomization	Censored
No on study tumor assessments and no death*	Date of randomization	Censored
Subsequent anti-cancer therapy started without death or progression per RECIST v1.1 reported prior or on the same day	Date of last evaluable tumor assessment prior to or on the date of initiation of the subsequent anti-cancer therapy	Censored
Documented progression per RECIST v1.1 and no new anti-cancer started before	Date of the first documented progression per RECIST v1.1 (excludes clinical progression)	Progressed

Table 4.1.3.1-1: Censoring Scheme used in Primary Definition of PFS

Situation	Date of Progression or Censoring	Outcome
No progression and no death, and no new anti-cancer therapy started	Date of last evaluable tumor assessment	Censored

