6.3 Populations for Analyses

- Enrolled subjects: All subjects who signed the informed consent form and obtained a subject number.
- Randomized subjects: All subjects who were randomized through the IRT.
- Treated subjects: All randomized subjects who received at least one dose of any study treatment.

Unless otherwise specified, the safety analyses will include all treated subjects.

Unless otherwise specified, the efficacy analyses will include all randomized subjects.

All analyses will be performed using the treatment arm as randomized (intent to treat), with the exception of dosing and safety, for which the treatment arm as received will be used. For purposes of analysis, the following populations are defined in Table 6.3-1.

Specific to this study, subjects may receive three types of chemotherapy regimen (as per investigator’s choice): XELOX, FOLFOX, or SOX. Chemotherapy regimen “as randomized” (referred to as “planned chemotherapy regimen”) will be retrieved from the IRT system. Chemotherapy regimen “as treated” will be, in general, the same as the planned chemotherapy regimen. However, if a subject received the other chemotherapy regimen for the entire period of treatment, the subject’s chemotherapy regimen will be defined as the regimen the subject actually received.

Table 6.3-1: Populations for Analyses

Population	Description
All Enrolled Subjects	All subjects who sign informed consent and were registered into the IRT.
All Randomized Subjects	All subjects who were randomized to either treatment arm. This population will be used for analyses of demography, protocol deviations, baseline characteristics, efficacy, and clinical outcomes assessments (must have baseline and on-study assessment).
All Treated Subjects	All subjects who received at least one dose of any study medication. This is the primary population for exposure and safety analyses.
All Treated LAG-3 Positive Subjects	All treated subjects in the LAG-3 positive ($\geq 1\%$) group. This is used for select disposition, exposure, and safety analyses.
All Treated LAG-3 Negative Subjects	All treated subjects in the LAG-3 negative ($<1\%$) group. This is used for select disposition, exposure, and safety analyses.
All Randomized LAG-3 Positive Subjects	All randomized subjects in the LAG-3 positive ($\geq 1\%$) group. This is the dataset for primary efficacy analyses.

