7.5.1 Analysis of Objective Response Rate (ORR)

Primary (and secondary) objectives of the study are to compare ORR per BICR between treatment groups among LAG-3 positive (primary objective) and among LAG-3 negative (secondary objective) randomized subjects.

[figure not shown]
The number and percentage of subjects in each category of BOR per BICR (complete response [CR], partial response [PR], stable disease [SD], progressive disease [PD], or unable to determine [UTD]) will be presented, by treatment group, for each LAG-3 population and overall. Estimates of response rate, along with its exact two-sided 95% CI by Clopper and Pearson¹¹ will be presented, by treatment group for each LAG-3 population and overall.

[figure not shown]
ORR as assessed by BICR will be compared between treatment groups using a two-sided Cochran-Mantel-Haenszel test stratified by PD-L1 status ((CPS $\geq 5\%$, CPS ≥ 1 to <5 , or CPS $< 1\%$ (including indeterminate)) as recorded in the IRT. These analyses and associated 70% CIs for ORR difference will be performed on the All Randomized LAG-3 Positive Subjects (primary population), All Randomized LAG-3 Negative Subjects, and All Randomized Subjects.

The following subject-level graphics will also be provided:

- For the responders only, time courses of the following events of interest will be graphically displayed: tumor response, progression, last dose received, and death
- For response evaluable subjects (defined per RECIST 1.1 as randomized subjects with baseline and at least one on-study tumor assessment)
 - A bar plot showing the best % reduction from baseline in sum of diameter of target lesions based on BICR assessment for each subject will be produced (excluding assessments after PD and assessments after start of subsequent anti-cancer therapy)
 - A plot of individual time course of tumor burden change per BICR assessment will be produced

Similar analyses will be repeated based on the investigator's assessment of ORR. A cross tabulation of BICR best response versus the investigator best response will be presented, by treatment group and by response categories. Concordance Rate of Responders will be computed as the frequency with which investigator and BICR agree on the classification of a subject as responder vs. non responder/UTD as a proportion of the total number of randomized subjects (using relevant populations) assessed by both the investigator and BICR.

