7.5.4 Analysis of Progression-Free-Survival

One of the objectives of the study is to assess the difference in progression-free survival (as determined by BICR) between treatment groups in the LAG-3 positive, LAG-3 negative, and all randomized populations.

The analysis of PFS (as determined by BICR) will be to compare the two treatment groups via stratified log-rank test among all randomized subjects at a two-sided $\alpha = 0.30$ level.

The primary definition of PFS adjusting for subsequent anticancer therapy will be used in this analysis.

The estimate of the PFS hazard ratio between treatment groups will be calculated using a stratified Cox proportional hazards model, with treatment as the sole covariate. Ties will be handled using the exact method. A two-sided 70% CI for the hazard ratio will also be presented.

The PFS function for each treatment group will be estimated using the KM product limit method and will be displayed graphically. A two-sided 95% CI for median PFS in each treatment group will be computed via the log-log transformation method.

These estimates will be derived from the Kaplan Meier estimate and corresponding CIs will

be derived based on Greenwood¹⁴ formula for variance derivation and on log-log transformation applied on the survivor function¹⁵.

[figure not shown]
The source of PFS event (progression or death) will be summarized by treatment group.

[figure not shown]
Analyses of PFS may also be conducted based on the secondary definition of PFS. These analyses will be the same as those specified above.

The status of subjects who are censored (as per primary definition of PFS) in the PFS KM analysis will be tabulated for each randomized treatment group including the following categories:

- On-study (on-treatment, in follow-up)
- Off-study (lost to follow-up, withdraw consent, never treated)
- No baseline tumor assessment
- No on-study tumor assessment and no death
- Received subsequent anticancer therapy

Similar analyses will be repeated based on the investigator's assessment of progression.

[figure not shown]

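### Central review is specified for treated participants, while BICR endpoints are analysed in all randomized; only BICR PFS in a few never-treated participants can be affected

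*Protocol*

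**What the plan says.** **Scope of reading.** Protocol 5.1.4: "The BICR will review all available tumor assessment scans for all treated participants". SAP 2.5 carries the same sentence. Protocol 10.2 defines treated as "All randomized participants who take at least 1 dose of study treatment", which is a subset of those randomized.

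**Scope of analysis.** SAP 6.3: "Unless otherwise specified, the efficacy analyses will include all randomized subjects". BICR ORR is "divided by the number of all randomized subjects" (SAP 4.1.1), and the primary version is "divided by the number of randomized participants who are LAG-3 positive in each arm" (protocol 10.3.2). BICR PFS is compared "via stratified log-rank test among all randomized subjects" (SAP 7.5.4).

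**Never-treated participants are expected.** Protocol 9.2.1 sets an SAE collection period for them. SAP 7.3.1 tabulates them by arm with reasons. SAP 7.5.3, 7.5.4 and 7.5.7 list them as a censoring status.

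**Other passages are broader than 5.1.4.** Protocol 9.1.1 runs on-study imaging from the date of randomization. Protocol 9.1.4 has sites send every scan to the core laboratory. The sentence in 5.1.4 that follows the one quoted puts all investigator-determined progressions before the BICR. SAP 7.3.2 reports baseline and target lesions by both investigator and BICR in the randomized populations. None of these is limited to dosed participants.

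**The concern.** Whether a participant is dosed is settled after randomization. The trial is open-label and dosing may start up to 3 calendar days after randomization (protocol 5.1.2), so a decision not to start can depend on the assigned arm. An as-randomized comparison should not let such an event decide whose scans the central reader sees.

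PFS is where this could matter. If a never-treated participant's scans are not read, a progression on them is invisible to BICR. The participant also has no BICR baseline read, and the SAP's censoring tables have a row for exactly that situation. It censors at randomization and does not require that the participant be alive.

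**Working it through.** No stated figure is in dispute, so the check is mainly a comparison of passages, followed by a bound on the number affected.

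**1. Who falls in the gap.** Randomized minus treated gives the never-treated.

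**2. Whether scans exist.** Baseline imaging within 28 days before randomization is an entry requirement (protocol 6.1). Later scans are acquired until BICR-confirmed progression, subsequent therapy, withdrawal or loss to follow-up (protocol 9.1.1). The scans are therefore acquired and submitted. On the literal wording, only the read is missing.

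**3. ORR.** An unread participant stays in the denominator without a confirmed CR or PR. SAP 4.1.1 stops counting responses at subsequent therapy, so a never-treated participant is in practice a non-responder whether read or not.

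**4. Concordance.** SAP 7.5.1 takes as its denominator the randomized subjects assessed by both readers, so unread participants are not in it.

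**5. PFS, primary definition (SAP 4.1.3.1).** The text rule is "Subjects who did not have any on study tumor assessments and did not die will be censored on their date of randomization". Investigator PFS uses the same rules with the assessor exchanged. For a never-treated participant, counting only what happens before subsequent therapy:

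| Situation | Investigator PFS | BICR PFS if read | BICR PFS if not read |
|---|---|---|---|
| No post-randomization scan, no death | Censored at randomization | Censored at randomization | Censored at randomization |
| Scan without progression, no death | Censored at last scan | Censored at last scan | Censored at randomization |
| Scan with progression, no death | Event | Event if BICR agrees | Censored at randomization |
| Death, no prior progression | Event at death | Event at death | Event by the text and the death row; censored at randomization by the no-baseline row |

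The first row is the same throughout; the other three can differ. In the last row, Table 4.1.3.1-1 conflicts with its own text, because the no-baseline row lacks the no-death condition that the next row has. Table 4.1.3.2-1 (secondary definition) has the same row. That definition ignores subsequent therapy, so there the ambiguity applies to a death at any time.

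**6. Number affected.** The base is 250 randomized. The enrolment figure built on it reproduces: 250 / (1 − 0.40) = 417, against about 420 stated. The never-treated share f is not given, so the count is 250 × f for assumed values:

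- f = 1%: 2.5
- f = 2%: 5
- f = 3%: 7.5
- f = 5%: 12.5

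At 1 to 3% this is about 3 to 8 participants. It bounds the number affected from above, because everyone in the first row of the table is included and does not change.

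**7. Power for ORR.** Never-treated participants do dilute ORR, but the all-randomized denominator causes this, and reading the scans would not remove it. As an illustration, assume ORR 50% against 65%, 125 LAG-3 positive participants (62.5 per arm) and two-sided alpha 0.30. With pooled SE 0.0884 and unpooled SE 0.0874, power = Φ((0.15 − 1.036 × 0.0884) / 0.0874) = Φ(0.668) = 74.8%. Multiplying both rates by (1 − f) gives 73.5% at f = 2% and 71.5% at f = 5%. These figures are the same under either wording of 5.1.4.

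**The case against.** The strongest reply is that the sentence is loose drafting and not a restriction. It does not say *only*. The passages on image acquisition, scan submission, review of investigator progressions and BICR baseline lesions all presuppose central reads from randomization onward. Details are left to the BICR charter, which is not among the documents and may already cover everyone randomized. This largely stands as an account of intent. It does not remove the conflict: no passage expressly extends reading to never-treated participants, and the same sentence appears in both documents.

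A second reply is that a first-line patient who declines assigned treatment will often go straight to other therapy. Protocol 9.1.1 then stops imaging, and primary PFS is censored at randomization under either reader. This stands, and it is why the effect is confined to the last three rows of the table.

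A third is that never-treated participants are reported by arm, so an imbalance would be visible, and that SAP 7.5 calls everything beyond the primary endpoint descriptive. Both are fair and limit the importance of the point. SAP 7.5.4 does still specify a PFS log-rank test at two-sided 0.30.

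**Conclusion.** The stated reading scope does not match the analysis set, and the passages should be reconciled. The consequence is small. ORR and responder concordance are unaffected, and no sample size, alpha or power figure changes. BICR PFS can change only for never-treated participants with a post-randomization scan before subsequent therapy, or with a death that the no-baseline row could censor at randomization. Under an assumed never-treated share of 1 to 3%, at most about 3 to 8 of 250 are affected. The share is an assumption; the documents give none.

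Three stronger conclusions are tempting and not supported:

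- *The BICR and investigator assessments are compared on different people.* The only comparison the SAP visibly specifies is on responses, and its concordance rate uses subjects assessed by both. PFS is merely repeated by investigator.
- *Investigator PFS keeps never-treated participants while BICR PFS drops them.* The censoring rules are identical, and without a later scan or a death both readers censor at randomization.
- *Every never-treated participant loses all BICR PFS information.* That would need each of them to have usable later scans or a death. The text rule also counts a death without progression as an event whether or not scans were read.

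**What to change.** Replace *treated* with *randomized* in the reading-scope sentence of protocol 5.1.4 and SAP 2.5, and confirm that the BICR charter says the same. If the charter already covers all randomized participants, the two sentences misdescribe it and still need correcting. Making the change before database lock avoids leaving the handling of never-treated participants to programming decisions.

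The cost is one word in each document and central reading of a handful of scans that sites already submit. With a BICR baseline read in place, the no-baseline row would no longer be triggered merely because a participant was never dosed.
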